PROTOCOL and SAP

The Role of Human Fibrinogen Concentrate (RiaSTAP) in Decreasing Blood Loss and the Need for Component Blood Therapy in Infants Undergoing Cardiopulmonary Bypass

National Clinical Trial (NCT) Identification Number: NCT02822599

December 7, 2017

Purpose of Study

The goal of the study is to determine whether the use of Human Fibrinogen Concentrate (RiaSTAP) will decrease blood loss and the need for component blood therapy in neonates and infants undergoing cardiopulmonary bypass. RiaSTAP will be administered after termination of Cardiopulmonary Bypass (CPB) at a dose of 70 mg/kg, in a prospective, randomized, controlled study. We hypothesize that the administration of RiaSTAP in this manner will reduce peri-operative bleeding and transfusion requirements.

Background

Severe postoperative bleeding is a serious complication after cardiac surgery and results in increased morbidity and mortality¹². The bleeding is often multifactorial and influenced by both surgical factors and impaired hemostasis. The impaired hemostasis after cardiac surgery may be caused by enhanced fibrinolysis, platelet (PLT) dysfunction and coagulopathy secondary to the exposure of blood to artificial surfaces, and the surgical trauma³.

In children less than 12 months old with congenital heart disease, bleeding after cardiac surgery is further complicated as the fibrinogen of these patients is qualitatively dysfunctional⁴. Moreover, the coagulation systems of neonates and children undergoing CPB are profoundly affected by hemodilution⁵ and by consumption⁶. As a result, neonates and young infants undergoing complex cardiac repairs often receive multiple units of blood products, both in the operating room (OR) and intensive care unit (ICU).

Preoperative fibrinogen concentration is an independent predictor of post-operative bleeding volume. Fibrinogen concentration, even when within the normal range, is a limiting factor for post-operative hemorrhage⁷. The prophylactic infusion of fibrinogen concentrate has been shown to reduce bleeding after coronary artery bypass graft (CABG) surgery without evidence of hypercoagulability⁸. Moreover, ROTEM FIBTEM test guided fibrinogen concentrate administration was associated with reduced transfusion requirements and 24 hour postoperative bleeding in patients undergoing aortic valve operations and ascending aortic reconstructions⁹.

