Our institution has been using RiaSTAP on this high-risk patient population since April 2013. In a separate, retrospective analysis our group has compared a group of 50 patients who received RiaSTAP with 50 age, diagnosis and procedure matched patients prior to April 2013. Our analysis demonstrates that there is a statistically significant reduction in the need for FFP and cryoprecipitate, without an increase in thromboembolic events, when RiaSTAP is used at a dose of 70 mg/kg.¹⁵

Criteria For Subject Selection

Number of subjects: 30

Gender of subjects: There are no gender-based enrollment restrictions for this study. Gender distribution should reflect the gender distribution of the patient population and the gender distribution of Congenital Heart Disease (CHD) in general which is slightly skewed towards male patients in a 60:40 ratio of males to females.

Age of Subjects: Age will range from full term (at least 37 weeks gestational age) newborns to 12 months old, inclusive.

Racial and Ethnic Origin: There are no racial and ethnic restrictions for this study.

Inclusion Criteria: All neonatal and infant cardiac patients presenting for open-heart surgery at Nicklaus Children's Hospital will be eligible for enrollment in the study.

Exclusion criteria: Patients who fall outside of the age range for the study will be excluded. Patients known to have had an anaphylactic or severe reaction to the drug or its components will not be enrolled. At the time of the rewarming ROTEM, any patient with a FIBTEM MCF > 15 mm, will be excluded.

Vulnerable subjects: Patients in the study population are neonatal and infant cardiac surgical patients and are considered vulnerable subjects.

Methods and Procedures

Randomization:

We plan to enroll 30 neonates and infants scheduled for elective cardiac surgery. Patients will be randomized to one of two groups with 15 patients in each group; Group 1 will receive an infusion of RiaSTAP, right after the termination of CPB at a dose of 70 mg/kg and

Group 2 will receive a placebo of Normal Saline 0.9% (NS) during the same time period. The volume of NS will be calculated to be the same volume that would be used IF the patient were receiving RiaSTAP. This will be the only difference between the groups.

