Both Groups will receive the normal standard of care both before and especially after this event. This will be the only event that is different for the two groups. To avoid selection bias, the Pharmacy will perform the randomization using Research Randomizer. Briefly, for each patient, a randomly generated integer between 1-30 will be produced. If the number is even, the patient will be assigned to Group 1. If the number is odd, the patient will be assigned to Group 2. The randomization process and schedule will be provided by the Principal Investigator's office, but the actual patient assignment will be done by Pharmacy.

All operating room and ICU personnel will be blinded to the patient's Group assignment. The only persons who will have access to the identity of the Group assignment from the time of randomization until 24 hours after surgery will be members of the Pharmacy staff. NONE of these individuals will be involved in patient care. The DSMB will be unblinded AFTER the study treatment period concludes (24 hours after surgery).

Endpoints:

Primary efficacy endpoints will be estimated as follows:

- postoperative bleeding (EBL) during the first 24 hours (hr) after surgery (cc/kg),
- the identity and total volume of transfused blood products (cc/kg) given in the peri-operative period, separated out into its components,
- hemoglobin concentration 2 hr. and 24 hr. after surgery and
- effects of fibrinogen infusion on global hemostasis 2 hr. and 24 hr. after surgery (PT, PTT, INR, fibrinogen level, platelet count and ROTEM analysis).

Post-operative period begins after the patient leaves the operating room. The need for Factor VII use and dose will also be included as a primary end point. Factor VII is typically used only if there is profuse bleeding not amenable to component transfusion therapy.

Secondary end points will include:

- the number of post-op hours requiring ventilator support,
- Length of Stay (LOSH) in the hospital,
- Length of Stay (LOS ICU) in the Cardiac Intensive Care Unit (CICU) and
- the need for re-exploration for bleeding within the first 12 hours.

The primary safety endpoints that will be monitored are the presence of a clinical adverse events. Clinical adverse events (AEs) are defined as any clinical signs of central or peripheral thromboembolism, respiratory or circulatory failure, or allergic reactions during hospital stay. It will also include infection with a blood-borne pathogen.

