To avoid selection bias, patients will be randomized to their treatment assignment group by the research pharmacists using the Research Randomizer. The randomization procedures are detailed in the Methods and Procedures section of this protocol. All operating room and ICU personnel will be blinded to the patient's Group assignment. An intensive care nurse blinded to group assignment will record postoperative bleeding every hour. Since the study is blinded and the practitioners caring for the patient will not know if the subject received the study drug or placebo, for the study treatment period (ending 24 hours after surgery), the Cardiac Intensive Care Unit staff will monitor the incidence of adverse thromboembolic events and intervene with routine care, if necessary. In order to maintain patient safety, the ROTEM analyses must be interpreted by the anesthesiologist caring for the patient in order to guide transfusion therapy. This is the standard of care and an integral part of the protocol. The hospital staff anesthesiologists are also investigators in the study including the Principal Investigator. As part of routine care, if the ROTEM results indicate a deficiency of platelets or FFP, either component will be administered while still in the OR. In addition, if the ROTEM indicates a fibrinogen deficiency after termination of CPB, cryoprecipitate will be given. After review of the ROTEM values, the identity of the study drug may be discernable. In order to avoid the ascertainment bias from this knowledge, study data will be analyzed by a biostatistician independent of the investigator prior to any presentation or publication of study results. The biostatistician will be blinded to the study treatment assignment.

Statistical Analyses

All quantitative measures will be analyzed using descriptive statistics [mean +/- standard deviation (SD), etc.]. Treatment and placebo group comparisons will be made with the Student's t-test (continuous variables) or Fisher's exact test (categorical variables). A p-value of ≤ 0.05 will be considered statistically significant. For group comparisons of variables that will be analyzed at more than onetime point, Analysis of Variance (ANOVA) for repeated measurements will be used followed by Student's t-test if the ANOVA (group or interaction between group and time) indicated a statistically significant difference ($p \leq 0.05$).

Data Storage and Confidentiality

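### At least nine measures are labelled primary efficacy and judged at p ≤ 0.05, with no single primary and no rule saying which result, or how many, would count as success

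*Combined protocol and SAP*

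**What the plan says.** The Purpose of Study states the question: "We hypothesize that the administration of RiaSTAP in this manner will reduce peri-operative bleeding and transfusion requirements".

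The Endpoints section opens its list in the plural: "Primary efficacy endpoints will be estimated as follows". The list holds:
- bleeding over the first 24 hours after surgery;
- "the identity and total volume of transfused blood products (cc/kg) given in the peri-operative period, separated out into its components";
- hemoglobin at 2 and 24 hours;
- "effects of fibrinogen infusion on global hemostasis 2 hr. and 24 hr. after surgery (PT, PTT, INR, fibrinogen level, platelet count and ROTEM analysis".

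The same section then makes Factor VII use and dose primary. Patient Assessment repeats the list, but mentions Factor VII only after the secondary endpoints and without a label.

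Statistical Analyses assigns Student's t-test or Fisher's exact test to group comparisons and sets the threshold: "A p-value of ≤ 0.05 will be considered statistically significant". Variables measured more than once first go through a repeated-measures ANOVA, and t-tests follow "if the ANOVA (group or interaction between group and time) indicated a statistically significant difference". No section names a lead endpoint, a testing order, a multiplicity adjustment or a success rule.

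The windows for the two clinical outcomes also differ:
- **Bleeding.** Under Endpoints, "Post-operative period begins after the patient leaves the operating room". Under Drug protocol, ICU bleeding is chest tube drainage from sternal closure through the first 24 postoperative hours, or over those 24 hours if the sternum stays open.
- **Transfusion.** It is peri-operative under Endpoints and recorded over the hospital stay under Drug protocol. Note 12 to the Schedule of Events also includes pump prime and bypass volumes.

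**The concern.** A reader of the final report could not tell from the plan which result makes the trial positive or negative. Followed as written, the plan would let a chance difference in blood loss, one blood product or one laboratory test be reported as a primary efficacy result. A higher fibrinogen level or a changed ROTEM value after an infusion of fibrinogen does not show that infants bleed less or need fewer transfusions, yet it would meet a listed primary endpoint.

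The choice between requiring one clinical outcome or both is also left open until after the data are seen, and the error rate depends on that choice. The differing windows add a further choice, which the percentages below do not count.

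**Working it through.** The plan states no overall error rate, effect size, SD or power, so it has no figure of its own to reproduce.

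**Inputs.** 15 infants per arm (Randomization); p ≤ 0.05 per comparison (Statistical Analyses). Sidedness is not stated; two-sided is assumed. The documents give no correlations between outcomes; 0 to 0.7 is assumed. Data are taken as normal.

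**1. Count.** Bleeding 1 + transfusion 1 + hemoglobin 1 + hemostasis 6 = 9. With the four products in place of one transfusion measure, the count is 12; with the total as well, 13. Factor VII adds one or two more under Endpoints. ROTEM is counted once, although the transfusion algorithm uses several of its parameters. Nine is therefore a minimum.

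**2. The two outcomes in the hypothesis.** With independent tests:
- at least one significant: 1 − 0.95² = 9.75%;
- at least one significant in the drug's favour: 1 − 0.975² = 4.9%;
- both significant: 0.05² = 0.25%.

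With correlated tests (bivariate normal):

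| Correlation | Either, two-sided | Either, favouring drug | Both |
|---|---|---|---|
| 0 | 9.75% | 4.9% | 0.25% |
| 0.3 | 9.5% | 4.8% | 0.5% |
| 0.5 | 9.1% | 4.5% | 0.9% |
| 0.7 | 8.4% | 4.2% | 1.7% |

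Simulated t-tests at 15 per arm agree to within about half a percentage point. At correlation 1 the either-outcome rate falls to 5%.

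**3. The ANOVA step.** For one laboratory variable measured at 2 and 24 hours under no effect, a t-test at either time is significant in about 8-10% of simulated trials. The ANOVA condition (group or interaction) is met in about 10%. Requiring the ANOVA and then a t-test gives 5.6-6.0%. The step therefore helps within a variable. It does nothing across variables, and it does not apply to 24-hour bleeding or transfused volume.

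**4. All nine measures.** Take INR as moving exactly with PT. That leaves two single-time measures at 5% and six distinct repeated measures at about 5.8%. At correlation 0:

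1 − 0.95² × 0.942⁶ = 1 − 0.9025 × 0.6987 = 36.9%.

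Simulation gives 36-38% at correlation 0 and 22-25% at 0.7. Favouring the drug, the figures are 20-21% and 11-13%. Counting INR as fully separate would give 1 − 0.9025 × 0.942⁷ = 41% at correlation 0.

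**5. Transfusion split by product.** Blood loss, four products and their total give 25% at correlation 0 and 15% at 0.7. These figures lean on normality. If a product is seldom used, most values are zero and the t-test is conservative. In an illustration with assumed use rates, its false-positive rate was 0.5% at 5% use, 2.5% at 10% use, and about 5% from 20% use.

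**The case against.** The strongest reply is that the hypothesis joins bleeding *and* transfusion, so both must improve. On that reading the false-positive rate is below nominal. It is a fair reading, and it rules out saying that the two outcomes carry an 8-10% error whatever the rule. But no section turns the conjunction into a decision rule, so either reading could be adopted after the results are known.

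Three further points limit the finding:
- The hypothesis is directional. Counting only errors in the drug's favour, the either-outcome rate is 4-5%. The comparison is then with 2.5%, so the rate still nearly doubles.
- The laboratory measures are not tested plainly at 0.05, because the ANOVA comes first. That is credited above.
- The figures that include single products may be too high where a product is rarely used.

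A reader might also infer that the 15-minute operating-room blood readings and the 24-hour mark for transfused products in the Schedule of Events are competing endpoint windows. The documents do not clearly support this. Drug protocol and note 5 tie the readings to the definition of clinically significant bleeding, and the mark can be read as a data-collection time. The mismatches that stand are those between Endpoints and Drug protocol, together with note 12 for transfusion.

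The small sample is no defence. The protocol does not call this trial a pilot, and it states both a directional hypothesis and a significance threshold.

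**Conclusion.** The point holds and should be fixed before results by arm are seen. The defect is not that no primary is named: many are, with none singled out and no rule for success. The labelling of Factor VII also differs between the two lists.

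The size depends on the missing rule. Inflation for the two outcomes in the hypothesis arises only if either one suffices; if both are required there is none. The 22-38% across nine measures is the rate if any listed primary may carry the claim. It assumes normal data, the correlation range above, and INR tied to PT. The absence of a success rule rests on the text alone and needs none of these assumptions.

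**What to change.** Before anyone sees results by arm:

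1. Limit the primary to 24-hour blood loss (cc/kg) and total transfused volume (cc/kg).
2. State one success rule: (a) one named primary at 0.05, with the other next in a fixed sequence; (b) Holm, if either suffices; or (c) each at 0.05, if both must succeed.
3. Make product volumes and Factor VII secondary. Report hemoglobin, coagulation tests, platelets, fibrinogen and ROTEM as mechanistic estimates with confidence intervals and no efficacy claim.
4. Make the Endpoints and Patient Assessment lists agree.
5. Give each of the two outcomes one start and one stop. For bleeding, reconcile Endpoints with Drug protocol, including its open-sternum case. For transfusion, reconcile Endpoints, Drug protocol and note 12.

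The cost is rewording and fewer confirmatory claims. At 15 per arm, a single t-test has 80% power for 1.06 SD at 0.05 and for 1.18 SD at 0.025 (noncentral t). By rule:
- **(a)** The second claim is lost if the first fails. The sponsor should choose the order knowing that the Background's summary of its retrospective comparison reports a "statistically significant reduction in the need for FFP and cryoprecipitate" and gives no bleeding result.
- **(b)** An outcome needs 1.18 SD for 80% power only if the other has no effect. With equal effects, each needs about 1.10-1.12 SD. With 1.06 SD on both, the chance of at least one success is about 91% at correlation 0 and 81% at 0.7.
- **(c)** With 1.06 SD on both, power is 64% at correlation 0 and 71% at 0.7.

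### The repeated-measures ANOVA that gates the 2 h and 24 h laboratory endpoints conventionally omits any infant lacking one value, and the plan states no rule for missing samples; a mixed model would use every value at almost no cost.

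*Combined protocol and SAP*

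**What the plan says.** The Endpoints section opens its list with "Primary efficacy endpoints will be estimated as follows". Besides bleeding and transfusion, that list includes hemoglobin at 2 h and 24 h and the "effects of fibrinogen infusion on global hemostasis 2 hr. and 24 hr. after surgery", measured by PT, PTT, INR, fibrinogen, platelet count and ROTEM. Patient Assessment repeats the list, and Table 1 schedules these samples at the same two hours.

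For any variable with more than one time point, Statistical Analyses says "Analysis of Variance (ANOVA) for repeated measurements will be used". Student's t-tests follow only if the group or group-by-time term is significant. The threshold is "A p-value of ≤ 0.05 will be considered statistically significant"; sidedness is not stated.

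On size, the Randomization section says "We plan to enroll 30 neonates and infants scheduled for elective cardiac surgery" and "Patients will be randomized to one of two groups with 15 patients in each group". No power, effect size, SD or missing-data rate is given. Nowhere do the documents define an analysis population, an imputation method or the handling of a missing 2 h or 24 h value.

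**The concern.** Conventional repeated-measures ANOVA needs a value at every time point. An infant with a valid 2 h fibrinogen but no 24 h fibrinogen then contributes nothing to the fibrinogen ANOVA. The t-tests could use that 2 h value, but they are reached only through the ANOVA.

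Two things are at stake. With 15 infants per arm, each loss takes a visible share of power. The loss may also be informative. The protocol itself anticipates cardiac arrest and early re-exploration, and either can fall between the two samples. If infants with poor 2 h values lose the 24 h sample more often in one arm, the completers no longer represent the arms as randomized.

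**Working it through.** **Inputs from the documents.** 30 infants, 15 per arm (Randomization); threshold 0.05 (Statistical Analyses); samples at 2 h and 24 h (Endpoints, Table 1).

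**Assumptions.** Two-sided tests, normal data, equal variance at both times, correlation ρ between the 2 h and 24 h values of 0.3, 0.5 or 0.7, and all missing rates. The documents give none of these.

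**The plan's own figure.** The sample size of 30 cannot be reproduced, because no effect, SD or power is stated. As a benchmark, 15 per arm gives 80% power at a difference of d = 1.06 SD.

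**1. Power among completers.** With two time points, the ANOVA group test equals a t-test on each infant's mean of the two values, so d is in SDs of that mean. The noncentrality is d × √(n/2) on 2n − 2 degrees of freedom.

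| Completers per arm | Noncentrality | Critical t | Power |
|---|---|---|---|
| 15 | 1.06 × √7.5 = 2.903 | 2.048 | 80.0% |
| 14 | 1.06 × √7.0 = 2.804 | 2.056 | 77.0% |
| 13 | 1.06 × √6.5 = 2.702 | 2.064 | 73.7% |
| 12 | 1.06 × √6.0 = 2.596 | 2.074 | 69.9% |

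Each infant lost per arm costs about 3-4 points.

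**2. How many might be lost.** If each sample is missed independently with probability p, expected completers are 30 × (1 − p)²: 28.8 at 2%, 27.1 at 5% and 24.3 at 10%. The plan does not say whether pre-operative or intra-operative values enter the ANOVA. At 5% per time, three times would leave 30 × 0.95³ = 25.7 and four would leave 30 × 0.95⁴ = 24.4.

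**3. What a mixed model recovers.** The table gives simulated power for the group effect at d = 1.06, with only the 24 h value missing, completely at random (5,000 trials per scenario).

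| 24 h missing | Completer ANOVA | Likelihood analysis | Recovered |
|---|---|---|---|
| 5% | 77-78% | 79-80% | 1-3 points |
| 10% | 75-76% | 79% | 3-4 points |
| 20% | 69% | 77-79% | 8-10 points |

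The likelihood column uses a Wald approximation that is 1-2 points optimistic.

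For the 24 h contrast alone the gain is smaller. With 13 of 15 observed per arm, the variance factor is (1 − ρ²)/13 + ρ²/15. At ρ = 0.3 this is 0.91/13 + 0.09/15 = 0.0760, an effective n of 13.2. At ρ = 0.5 and 0.7 the effective n is 13.5 and 13.9. Power is then about 74%, 75% and 77%, against 73.7% for completers.

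**4. Bias when the loss is informative.** As an illustration, suppose infants more than 1 SD below the control mean at 2 h miss the 24 h sample 80% of the time, and the true differences are 1.0 SD at 2 h and 0.5 SD at 24 h.

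- Controls below the cut: 15.9%. Expected losses are 15 × 0.8 × 0.159 = 1.9.
- Treated below the cut: 2.3%. Expected losses are 15 × 0.8 × 0.0228 = 0.3.
- Among completers the control mean rises by 0.8 × 0.2420/(1 − 0.8 × 0.1587) = 0.222, and the treated mean by 0.8 × 0.0540/(1 − 0.8 × 0.0228) = 0.044.
- 2 h difference among completers: 1.0 − 0.222 + 0.044 = 0.82. From all available 2 h values it is 1.00.
- 24 h difference among completers: 0.5 − ρ × 0.178, which is 0.45, 0.41 and 0.38 at ρ = 0.3, 0.5 and 0.7. The likelihood estimate is 0.50.

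Simulation of 20,000 trials agrees to within 0.01.

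**5. Where the remedy stops.** In a harsher case, only placebo infants with low values miss 24 h, and they are 10% of all infants. If the loss depends on the 2 h value, completer bias in the group effect is about −0.28 SD and likelihood bias about 0. If it depends on the unseen 24 h value, the likelihood analysis is still biased by −0.10 to −0.14 SD. With no treatment effect and the same mechanism in both arms, neither method shows bias (within 0.01 SD).

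**The case against.** The strongest reply is that the plan never says incomplete infants are dropped. That is right: omission is the method's convention, and the documented gap is the lack of any missing-data rule. The gap still has to be filled, and convention would fill it this way.

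A reader might infer that the trial would report a 2 h difference of 0.82 where the truth is 1.0. The documents do not support this. Descriptive statistics and t-tests are not restricted to completers, and at 2 h they are unbiased on all available values. What remains exposed is the ANOVA gate and the 24 h comparison.

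A reader might also take the fall from 80.0% to 73.7% as the gain from a mixed model. It is not: it compares completers with full data, and the recoverable part is the smaller figure in step 3.

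The mechanism is also open to challenge. Both samples fall within 24 h of surgery, in monitored inpatients with arterial and central lines, and a return to the operating room need not lose a sample. Nothing in the documents supports the 80% missing rate. Low values are the unfavourable direction for fibrinogen or platelets but not for PT, PTT or INR, and a loss concentrated in controls presumes that the treatment works. These points stand. They limit the size of the problem but do not favour the planned method, since on complete two-time data the two analyses agree.

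**Conclusion.** The point holds as an inexpensive improvement to the analysis of the laboratory endpoints. It is not a threat to the trial's main aim, because blood loss and transfusion volumes are totals and do not pass through this ANOVA.

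For the laboratory variables, an unstated missing-data rule meets a method that conventionally needs complete cases. The cost is about 3-4 points of power per infant lost per arm at the benchmark effect, of which a mixed model recovers about 1-4 points at 5-10% missing at random. Bias arises only if loss depends on the value and differs by arm. The 24 h figure of 0.38-0.45 against a true 0.5 illustrates this under assumed rates and is not a forecast.

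It would be too strong to say that a mixed model avoids the bias. That is true only if data are missing at random given the observed values. Samples lost to death or circulatory failure may not be, and then bias is reduced without being removed. The documents give no missing rate, so the actual size cannot be established from them.

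**What to change.** Replace the repeated-measures ANOVA with a linear mixed model on all observed values. Use fixed effects for arm, time and arm-by-time, an unstructured covariance over time, and Kenward-Roger degrees of freedom. Read the arm differences at 2 h and 24 h directly from this model. Name the time points that enter it.

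State how values after a death and samples that could not be obtained are handled. A likelihood model otherwise implicitly supplies a 24 h value for an infant who has none. Report missing samples by arm and reason. If more than a few are missing, add a simple missing-not-at-random sensitivity analysis, for example by shifting the assumed missing values in one arm over a stated range.

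The cost is a short paragraph of SAP text and a few lines of code, with no extra data. The drawback is reliance on missing-at-random given the observed values. That is a weaker assumption than the completer ANOVA makes, but it cannot be checked from the data.
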